In order to lay the groundwork for a future Merit Review proposal investigating the utility of spatial cognitive training in visual rehabilitation, the currently proposed SPiRE project seeks to establish the feasibility of such training in visually impaired participants over a telehealth interface, to obtain data on the effect size of the training relative to a control intervention to provide a basis for sample size estimation in a larger clinical trial, and to examine the relevant neural mechanisms so as to suggest possible synergistic interventions that would enhance the effects of spatial cognitive training. Importantly, the proposed work will examine the real-world generalizability of the training effects using physical walking spaces to assure relevance to rehabilitation.

Research Design and Methods

PARTICIPANTS

We will recruit 60 blind participants, randomized by our CVNR statistician into two groups. One group will undergo the experimental intervention (spatial cognitive training) and the other will undergo a control intervention involving letter-number matching. The participants will include women and minorities in proportion to the demographics of the veteran population attending the Atlanta VA. Working with our statistician, we calculated that this sample size has a power of 0.81 to detect an effect size of 0.9 with $\alpha=0.05$ and $\beta=0.19$. The randomization process should result in a balance between the intervention and control groups with respect to a range of variables, including age, sex, age of onset of visual loss, duration of visual loss and of loss of light perception, and comorbid conditions; any residual differences will be accounted for as covariates in statistical analyses.

Since the participants are blind or have low vision, they will need transportation to the CVNR, which will be provided via a contractual arrangement in place with the CVNR. Subjects will be compensated for their time at a flat rate of \$150 for participation in all sessions of the study. If they drop out or are otherwise unable to complete the study, compensation will be prorated for the number of sessions they participate in.

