Participants will be enrolled after signing informed consent according to protocols approved by the local IRB and R&D Committee. They will be recruited from a registry of visually impaired persons maintained by the CVNR, the Ophthalmology and Low Vision clinics at the Atlanta VA, as well as the community secondary to difficulty in recruiting a sufficient number of subjects from the Atlanta-based veteran population. An advertisement will be placed on the CVNR website. Based on projections modeled by [name], of the VA Blind Rehabilitation Service National Program Office, we estimate that in 2015 there are approximately 234 veterans with no light perception in the counties constituting the catchment area of the Atlanta VAMC, with this prevalence estimated to increase to 249 in 2020. Thus, we anticipate no difficulty with recruiting the required number of blind participants for this study. The research assistant will make contact with visually impaired subjects in the IRB-approved CVNR registry and with appropriate patients seen at the Atlanta VAMC Eye Clinic and Low Vision Clinic and Emory Eye Center to screen them for potential eligibility, and recruit eligible subjects. We have experience using these methods to recruit subjects for studies at the CVNR.

PROCEDURES

Specific Aim I will test the hypothesis that spatial cognitive training of blind participants on a spatial imagery task leads to improvements in **(a)** performance on the trained spatial imagery task and **(b)** real-world navigational ability, relative to a control intervention. **Specific Aim II** will use fMRI to assess the neural changes associated with spatial cognitive training, as assessed by the spatial imagery task. The hypothesis is that those in the spatial cognitive training group will show enhanced activation in and connectivity of brain regions mediating spatial processing, such as the hippocampus and dorsal frontoparietal cortex, as well as more distinct neural representations of imagined paths.

[figure not shown]

[figure not shown]
Figure 2. Study flow.

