Interventions: The experimental intervention (spatial cognitive training) will comprise repeated practice of the spatial imagery task with feedback after each trial. Training will be conducted in the participant's home using an iPad issued to the subject at the initial visit, and live video communication with a research assistant at the CVNR over the internet. The iPad will be programmed to allow administration of the spatial imagery task. As in the version of the spatial imagery task administered at initial and final testing, audio cues will trigger mental navigation through the grid using audio cues, with haptic reinforcement via tactile overlays for the screen (to permit sensory facilitation of learning). Following each sequence traced, subjects will be asked whether the shortest path back to the origin intersects with the sequence traced or not. If the answer is incorrect, the research assistant will show the correct path for the subject to trace mentally and haptically. In the control intervention, subjects will be taught letter correspondences to the numbers (e.g. 1->A, 2->B and so on until 25->Y), using a similar setup and procedure as in the experimental intervention.

Behavioral measures: The following behavioral measures will be collected before and again after training with the experimental and control interventions: (1) Performance (directional accuracy and response time [RT]) on the spatial imagery task will be acquired during fMRI scanning. (2) In addition, pointing accuracy will be measured on the real-world path integration task in the MSL, in terms of the angular difference between the target of pointing and the actual initial position. (3) We will also measure performance, with standardized neuropsychological tests, at baseline as well as at post-training, on (a) spatial memory using a haptic version (produced in the [name] lab using textured blocks) of the Corsi block test (Kessels et al., 2000), (b) the verbal memory tests of immediate and delayed memory from the RBANS (Randolph, 1998) and (c) verbal working memory tested by the Forward and Backwards Verbal Digit Span test from the Wechsler Adult Intelligence Scale (Wechsler, 2008). A research assistant will be trained by the PI and [name], Co-investigator on this project, to administer all the tests, as well as the training procedures.

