We predict that spatial cognitive training, but not the control intervention, will lead to improvements in performance on the spatial imagery task, its analog in the MSL, and the various functional neuroimaging measures. There may be transfer of spatial learning to the spatial memory task, but we do not expect transfer to the verbal memory and working memory measures, indicating the spatial specificity of training. We hypothesize that spatial cognitive training, but not training on the control intervention, will lead to increases in activation in cortex along the IPS and in the FEFs as well as in the hippocampus, increased strength of connectivity between these regions in the task and resting states, and also to more differentiated representations between different paths (i.e. their representations will show higher dissimilarity). The behavioral and neuroimaging measures obtained at baseline, including DTI measures of structural connectivity between the activated brain regions, will be tested as regressors to establish whether they predict changes in the repeated measures. This will be useful to examine the impact of individual differences in pre-training spatial and verbal abilities on the effects of training, and in the design of further studies aimed at targeting interventions tuned to individual performance in specific domains.

TIMELINE

First 2 months: Set up tasks and initiate recruitment

Next 20 months: Test and train 2 subjects per month, one in each group

Last 2 months: Analyze data and prepare publications

FUTURE DIRECTIONS

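### The timeline's one-per-arm-per-month rule, with no concealment stated, could make up to half of the allocations it covers predictable to the staff who recruit

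*Combined protocol and SAP*

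**What the plan says.** Allocation is touched on in two places. PARTICIPANTS states: "We will recruit 60 blind participants, randomized by our CVNR statistician into two groups". For the 20 months after set-up, TIMELINE states: "Test and train 2 subjects per month, one in each group". Neither these sections nor any other gives the method of sequence generation, a block size, the means of concealment, or the point at which an assignment is released.

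The staffing passages bear on who could use a predictable sequence:

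- The recruitment paragraph before PROCEDURES has the research assistant contact people in the registry and clinics "to screen them for potential eligibility, and recruit eligible subjects".
- Under Interventions, a research assistant conducts the training by live video and so knows the arm.
- Under Behavioral measures, a research assistant is to be trained "to administer all the tests, as well as the training procedures".
- Under Recruitment and informed consent, consent is taken by a trained staff member, not further identified.

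Study flow puts the first training session on the Monday after the initial session. PARTICIPANTS adds that residual group differences will be handled as covariates.

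**The concern.** A rule that each month contributes one participant to each arm is a permuted block of two, the most predictable permuted block. Once the first assignment of a pair can be seen, the second is certain. Here the role that would see it, by giving the training, also decides whom to approach next and when. The exclusion for more than minimal white matter disease leaves some further discretion, because the threshold is not defined and scans taken during the study count towards it.

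The Aim I test is the group-by-session interaction, so a stable difference in level between the groups cancels. Harm would come from selecting people by how much they are expected to improve. The protocol treats that as foreseeable: Background says individual differences matter in spatial training, and ANALYSES will test baseline measures as predictors of change. Preliminary Studies also says the estimated effect will be used to size a larger trial, so any bias would carry forward.

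**Working it through.** **The plan's own figures.** The documents give no figure for predictability. They do give a power statement: "this sample size has a power of 0.81 to detect an effect size of 0.9". I read 0.9 as a standardized difference, with 1:1 allocation and two-sided α = 0.05. By the normal approximation, power = Φ(0.9·√(n/2) − 1.96), with n per arm:

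- n = 30 (60 in total): Φ(3.486 − 1.96) = 0.936; by noncentral t, 0.929.
- n = 20 (40 in total): Φ(2.846 − 1.96) = 0.812; by noncentral t, 0.792.

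The stated 0.81 is reproduced at 40, not at 60. The timeline gives 20 × 2 = 40. Sixty in 20 months needs 60/20 = 3 per month, which cannot be split one to each arm. The pairing line therefore fits a 40-participant plan, and the count below is for 40.

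**Is the line a real constraint?** Under unrestricted 1:1 randomization, two participants fall in different arms with probability 1/2. All 20 months would do so with probability (1/2)^20, about one in a million. Following the line every month therefore requires balanced pairs.

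**Share of allocations known in advance.** This assumes sequential entry, earlier assignments visible and block size known. An allocation is certain when one arm's places in the block are used up. Exact enumeration gives:

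| Block size | Certain in advance | Best guess correct |
|---|---|---|
| 2 | 50% | 75% |
| 4 | 33.3% | 70.8% |
| 6 | 25% | 68.3% |
| 8 | 20% | 66.6% |

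For pairs, the first member is a coin toss and the second is certain, so the guess rate is (0.5 + 1)/2 = 0.75. Over the timeline, 0.50 × 40 = 20 allocations are certain. If both members are enrolled before either is allocated, or the assistant cannot see the pairing, the number is 0.

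**What steering could do (illustration only).** Suppose every known slot is filled by someone whose expected change is shifted by d SD in favour of training. Half of each arm is shifted, in opposite directions, so the bias is d/2 + d/2 = d. Simulated two-sided type I error for a t-test on change (4,000 runs per cell, 40 participants, no training effect) is:

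| Assumed d | Pairs | Known blocks of 4 |
|---|---|---|
| 0 | 0.05 | 0.05 |
| 0.1 | 0.06 | 0.05 |
| 0.25 | 0.11 | 0.08 |
| 0.5 | 0.32 | 0.17 |

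The documents give no value for d. These rows are worst cases, because they need successful steering in every known slot.

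**Cost of varying blocks.** With blocks of 4, 6 and 8, the largest imbalance when enrolment stops at 60 arises if the last block is an unfinished 8 whose first four places all went to one arm. That is a difference of 4, or 28:32. The variance factor 1/n₁ + 1/n₂ rises from 1/30 + 1/30 = 0.0667 to 1/28 + 1/32 = 0.0670. Power by noncentral t at 0.9 goes from 0.929 to 0.928.

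**The case against.** The line stands in a timeline between set-up and analysis and speaks of testing and training, not of allocating. The allocation statement is the one in PARTICIPANTS, and it gives the task to the statistician. A reader might infer from the timeline that blocks of two are the randomization method and that every second allocation in the trial is known beforehand. The documents do not support that: they never state a block size, and the line cannot generate 60 participants.

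Sequential entry is also an assumption. Training alone takes three weeks, so if both members of a pair were tested and trained within the same month they would start within about a week of each other. The second might already be recruited when the first begins training.

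A reader might further infer that one person holds all the roles. The eligibility text speaks of a single project research assistant, which suggests it, but no section says so outright. Nor do the documents show that bias of any given size would follow.

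All of this stands, and it limits the point to a conditional one. It does not remove it. The monthly one-per-arm clause is the only constraint on allocation that the plan states, and nothing says how assignments are hidden. A list prepared by the statistician does not by itself hide the next assignment if staff know that months are balanced. Covariate adjustment cannot correct selection on characteristics that are not measured.

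**Conclusion.** The point holds in conditional form. If the timeline is followed literally and the members of a pair enter one after the other, up to 20 of the 40 allocations it covers are predictable to the role that recruits, trains and tests. If the line is workload only, or both members are enrolled before either is allocated, that number is zero. The documents do not say which applies.

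The size of any resulting bias is unknown, and the figures for assumed shifts are not estimates. Still, this is more than missing detail, because the one constraint stated is the permuted block with the largest share of certain allocations. It should be changed, since the risk can be reduced at almost no cost.

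**What to change.** In TIMELINE, give an average of two participants per month and drop the one-per-arm clause. At the same time, reconcile the 40 that the timeline yields with the planned 60, and either with the stated power.

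In PARTICIPANTS, state that the statistician holds a single concealed list with randomly varying block sizes (for example 4, 6 and 8) not disclosed to study staff. State that each assignment is released only after consent, confirmed eligibility (including any MRI finding that could exclude) and all baseline testing are complete.

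The cost is protocol wording and, if needed, a new list, with no extra participants or staff. The downside is slight imbalance, at most 28:32 at 60 participants, with power at 0.9 moving from 0.929 to 0.928. If the list already works this way, only the description has to be added.
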